1.4. Safety Data Analysis

The primary assessment of safety will be based on the frequency of treatment-emergent adverse events (TEAEs), serious adverse events (SAEs) and on the frequency of clinically notable abnormal vital signs, electrocardiograms (ECGs) and laboratory values. Other safety evaluations include changes in vital signs, changes in clinical laboratory assessments, and changes in ECGs, physical exam findings during treatment, and suicide ideation (C-SSRS) and behavior events.

1.4.1. Adverse Events

Adverse events will be recorded throughout the study and at early discontinuation. Adverse events and medical conditions will be coded using the Medical Dictionary for Regulatory Activities (MedDRA) coding dictionary. Treatment-emergent adverse events will be defined as those events, which are newly occurring or worsening from baseline. In all cases, only treatment emergent adverse events will be summarized.

Treatment-emergent adverse events will be summarized within each treatment group by primary system organ class and preferred term. (**NOTE:** In any given category [e.g., body system], a patient will only be counted once.) The incidence rates of TEAEs will be analyzed as described in the SAP. Similar displays will be provided for SAE and prior (conditions ending prior to the first dose of study medication) and current (conditions present while on study medication) medical conditions.

Adverse events will further be categorized by severity, relationship to study medication, and action taken. Other information collected will be listed, as appropriate. Any event starting more than 3 days after the final dose of study medication will be excluded from the above tables and only listed unless the event caused discontinuation.

The proportions of patients experiencing SAEs and AEs resulting in discontinuation from the study will be summarized by treatment groups.

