This is multicenter, randomized, double-blind, placebo-controlled study to be conducted in the United States. Approximately Two Hundred (200) patients diagnosed with mild atopic dermatitis, who satisfy the eligibility criteria for the study, will be randomized to receive either tradipitant 85 mg or matching placebo BID.

The study is divided into two phases: the pre-treatment phase and the evaluation phase. The pre-treatment phase includes a screening and a baseline visit where patients' eligibility for the study will be assessed. Washout of medications will occur during the screening phase.

The evaluation phase includes 8 weeks of randomized, double-blind, placebo-controlled treatment. In-clinic evaluations will occur at Screening, Baseline, and Weeks 2, 4, 6, and 8.

Criteria for Evaluation:

Efficacy:

Efficacy assessments will include:

- Worst Itch Numerical Rating Scale (WI-NRS)
- SCORing Atopic Dermatitis (SCORAD) index
- Validated Investigator Global Assessment scale for Atopic Dermatitis (vIGA-AD)
- Eczema Area and Severity Index (EASI)
- Clinical Global Impression of Change (CGI-C)
- Patient Global Impression of Change (PGI-C)
- Patient Oriented Eczema Measure (POEM)
- Dermatology Life Quality Index (DLQI)
- Patient Benefit Index Pruritus (PBI-P)
- Insomnia Symptom Questionnaire (ISQ)
- Healthy Days Core Module (4 questions) (HRQOL-4)

Safety:

- Safety and tolerability assessments will include the recording of adverse events (AEs), physical examinations, clinical laboratory assessments, vital signs, and electrocardiograms.
- The Columbia-Suicide Severity Scale (C-SSRS) will be used to assess suicidal behavior and ideation.

Table 1: Schedule of Evaluations

Phase	Pre-Tre	Pre-Treatment		Evaluation				
Visit	V1 Screening	V2 Baseline	V3	V4	V5	V6		
Study Day	Up to Day -45	Day 0	Day 14 ¹	Day 28 ¹	Day 42 ¹	Day 56 ¹ or ET		
Informed Consent Form (ICF) ²	X							
Eligibility assessment	X	X						
Patient demography	X							
Medical history	X							
Prior/concomitant medications	X	X	X	X	X	X		
Adverse Event (AE) Assessment ³	X	X	X	X	X	X		
Serum β-HCG (for WOCBP)	X					X		
Urine pregnancy test (for WOCBP)		X	X	X	X			
HbA1c	X							
Hepatitis B/C screen	X							
Drug and alcohol screen	X	X	X	X	X	X		
Hematology, chemistry, and urinalysis ⁴	X	X	X	X		X		
Coagulation ⁴	X							
IgE collection	X	X	X	X	X	X		
Cytokine Panel ⁵	X					X		
Filaggrin Analysis ⁶	X							
Pharmacogenetic (PG) sample ⁶	X							
Pharmacokinetic (PK) sample		X	X	X	X	X		

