Resting 12-lead ECG	X	X	X	X	X	X		
Vital signs and body measurements ⁷	X	X	X	X	X	X		
Physical Examination (PE) ⁸	X	X	X	X	X	X		
Columbia-Suicide Severity Rating Scale (C-SSRS) ⁹	X	X	X	X	X	X		
Medical History of Pruritus Questionnaire		X						
Medical History of Atopy Questionnaire	X							
Pruritus Assessment (incl. NRS, VRS)	X	X	X	X	X	X		
SCORing Atopic Dermatitis (SCORAD) index	X	X	X	X	X	X		
Eczema Area and Severity Index (EASI)	X	X	X	X	X	X		
Validated Investigator Global Assessment scale for Atopic Dermatitis (vIGA-AD)	X	X	X	X	X	X		
Patient Benefit Index – Pruritus (PBI-P) ¹⁰		X	X	X	X	X		

Phase	Pre-Treatment		Evaluation			
Visit	V1 Screening	V2 Baseline	V3	V4	V5	V6
Study Day	Up to Day -45	Day 0	Day 14 ¹	Day 28 ¹	Day 42 ¹	Day 56 ¹ or ET
Patient Global Impression of Change (PGI-C)			X	X	X	X
Clinical Global Impression of Change (CGI-C)			X	X	X	X
Patient Oriented Eczema Measure (POEM)	X	X		X		X
Dermatology Life Quality Index (DLQI)	X	X	X	X	X	X
Insomnia Symptom Questionnaire (ISQ)	X	X		X		X
Healthy Days Core Module (4 questions) (HRQOL-4)	X	X		X		X
Daily Diary	←					*
Photography		X		X		X
Randomization		X				
Study medication dispensation ¹¹		X	X	X	X	
Study medication collection & compliance			X	X	X	X
Daily diary distribution and instruction	X					
Patient daily diary review		X	X	X	X	X

- 1 Within +/- 3 days.
- 2 Informed Consent will be obtained prior to performance of any study procedure(s).
- 3 Adverse Event collection will begin at the time the ICF is signed.
- 4 If elevated liver enzymes are present at any study visit, an unscheduled visit to redraw chemistry and coagulation samples will be completed prior to the next scheduled visit.
- 5 If the V1 cytokine panel sample is missed, the sample should be drawn at the next in-clinic visit (ex. V2).
- 6 If either the V1 Filaggrin or PG sample is missed or unable to be performed for any reason, the samples should be drawn at the next in-clinic visit (ex. V2).
- 7 Body height will only be collected at V1; body weight will be collected at V1, V2, and V6.
- 8 An abbreviated physical examination will be performed at V2-V5 ONLY if clinically indicated.
- 9 The Baseline C-SSRS will occur at V1. The Since Last Visit C-SSRS will occur at all other visits.
- 10 At V2, the Patient Needs Questionnaire (PBI-P(PNQ)) will be administered. The Patient Benefits Questionnaire (PBI-P(PBQ)) will be administered at subsequent visits.

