1.4.5. Columbia-Suicide Severity Rating Scale (C-SSRS)

Results from the C-SSRS will be listed for each patient. These data will also be summarized by treatment group and for suicidal ideation events, suicidal behaviors, and completed suicides. In particular, for each of the following suicide related events, the number and percent of patients with the event will be enumerated by treatment group: completed suicide, nonfatal suicide attempt, interrupted attempt, aborted attempt, preparatory acts or behavior, active suicidal ideation with specific plan and intent, active suicidal ideation with some intent to act without specific plan, active suicidal ideation with any methods (no plan) without intent to act, non-specific active suicidal thoughts, and wish to be dead. Details of the analysis will be provided in the SAP.

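### The 3-day cut-off in SAP 1.4.1 exempts events that caused discontinuation but not serious events, so a collected late SAE can be listed yet missing from the by-arm SAE display

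*SAP*

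**What the plan says.** SAP 1.4 sets the role of serious events: "The primary assessment of safety will be based on the frequency of treatment-emergent adverse events (TEAEs), serious adverse events (SAEs", together with clinically notable vital signs, ECGs and laboratory values.

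SAP 1.4.1 then proceeds in this order:

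1. Collection: "Adverse events will be recorded throughout the study and at early discontinuation".
2. Definition: an event is treatment-emergent if it is new or has worsened relative to baseline. No upper time limit after the last dose is given, and only treatment-emergent events are summarised.
3. Tables: treatment-emergent events by arm, system organ class and preferred term.
4. SAE tables: "Similar displays will be provided for SAE".
5. Cut-off: all those with onset beyond "3 days after the final dose of study medication will be excluded from the above tables and only listed unless the event caused discontinuation".
6. Proportions: "The proportions of patients experiencing SAEs and AEs resulting in discontinuation from the study will be summarized by treatment groups".

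The Protocol synopsis states "In-clinic evaluations will occur at Screening, Baseline, and Weeks 2, 4, 6, and 8". Table 1 allows 3 days either side of each visit after baseline. The last visit shown is V6, at Day 56 or early termination (ET).

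**The concern.** A short on-treatment window is common for routine adverse event tables, because it keeps off-drug background events from diluting the comparison. Serious events are usually treated differently, because they are few and each one matters. Here the window covers every event, and the only way back into the tables is that the event caused discontinuation. The drafter evidently saw that some late events belong in the tables, but chose a criterion that does not depend on seriousness.

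That criterion helps little in the cases at issue. An event that starts more than 3 days after the final dose cannot be the reason the patient stopped drug; at most it is the reason the patient left the study. A patient already off drug who has a nonfatal SAE and still attends the next visit does not meet it. The text does not say how a death after drug stop is classified for this purpose.

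At stake is whether the by-arm SAE display, which supports the primary safety assessment, counts every treatment-emergent SAE that was collected, and whether a reader can tell which SAE count carries the 3-day limit.

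**Working it through.** The plan gives no figure on this point, so there is none to reproduce. The check is a reading of the text, followed by simple arithmetic for scale.

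**Does the cut-off reach the SAE display?** Yes. The SAE display (item 4 above) comes before the cut-off (item 5), which applies to the tables already described. The cut-off covers any event and has one exemption, for events that caused discontinuation.

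**Is a late SAE otherwise eligible?** Yes. The definition of treatment-emergent has no end date, so a new SAE starting, say, 5 days after the last dose is treatment-emergent and yet is removed from the display.

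**Does the proportion sentence restore it?** That depends on the reading. The sentence follows the cut-off and states no window.
- If it means all SAEs, plus adverse events leading to discontinuation, the late SAE is counted by arm there. The two by-arm SAE summaries can then differ, with no explanation in the plan.
- If it means only SAEs and adverse events that led to discontinuation, the plan states no by-arm SAE count free of the window.

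**Is there a comparable count without the window?** For suicidal events, yes. In SAP 1.4.5, "the number and percent of patients with the event will be enumerated by treatment group: completed suicide, nonfatal suicide attempt" and further categories, with no 3-day limit. Table 1, footnote 9, adds: "The Since Last Visit C-SSRS will occur at all other visits". A nonfatal attempt more than 3 days off drug but before V6/ET, if also reported as an SAE, could be counted there and be missing from the SAE display.

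**Illustration of exposed time.** Inputs are the Table 1 visit days (0, 14, 28, 42, 56) and the 3-day visit window. Excluded days = max(0, gap from final dose to last contact − 3).
- Last dose on Day 56, V6 at its latest on Day 59: gap 3, excluded 3 − 3 = 0.
- ET visit within 3 days of the final dose: excluded 0.
- Assumed path: final dose on a visit day, next contact at the following scheduled visit. Nominal gap 14, excluded 14 − 3 = 11.
- Same path with both visits at the ends of their windows: gap 14 − 6 = 8 to 14 + 6 = 20, excluded 5 to 17.
- Same path from Day 0 to V3, where only V3 has a window: gap 14 − 3 = 11 to 14 + 3 = 17, excluded 8 to 14.

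**Effect per patient.** Assuming all 100 patients in an arm are in the Safety population, one patient whose only SAE is omitted changes the rate by 1/100 = 1.0 percentage point, and two by 2/100 = 2.0. If none is affected, the change is 0.

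**The case against.** The strongest reply has four parts.

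- **A by-arm SAE count may already exist.** If the proportion sentence covers all SAEs, a late SAE is counted there, and the loss is confined to the breakdown by system organ class and preferred term. This stands as a limit on the point. It does not put the event back into the SAE display, and the sentence would still need clarifying.
- **The text is general and incomplete.** SAP 1.2 defers the full methodology to a later statistical analysis plan, and the supplied protocol text does not include SAE reporting, post-dose SAE follow-up or ET timing. This limits what can be said about reach. It does not remove the wording problem, because the cut-off is stated outright and not deferred.
- **The case is narrow.** The patient must stop drug, be followed for more than 3 days, have an SAE that is collected, and not discontinue because of it. This stands, and it is why the severity is low.
- **A prespecified window, the same in both arms and backed by a listing, is a legitimate choice.** This is accepted for routine tables. It is less persuasive for SAEs, whose frequency is part of the primary safety assessment. The C-SSRS comparison is supporting only: a separate instrument may differ from an adverse event table without contradiction.

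A reader might infer that 17 days is the maximum excluded time. The documents do not support that. It describes one assumed path; a patient kept on study off drug, or SAE follow-up after V6 in text not supplied, could exceed it. A reader might also infer that serious events are concealed or that the comparison is biased towards one arm. Neither follows: every such event is listed, and the rule is the same in both arms.

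**Conclusion.** The point holds as a gap in the reporting rule. Followed exactly, SAP 1.4.1 leaves a collected, treatment-emergent SAE out of the by-arm SAE display if it starts more than 3 days after the final dose and did not cause discontinuation. Whether another by-arm count includes it depends on an ambiguous sentence.

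The number of patients affected cannot be derived or bounded from the documents, because the stopping rate, ET timing and any post-dose SAE follow-up are not given. It may be zero, and the effect is about 1 percentage point for each affected patient per 100. The excluded days above are an illustration only. No efficacy or power result is touched. Severity is low; the case for acting is that the events are serious and the correction is nearly free.

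**What to change.** Amend SAP 1.4.1 before unblinding:

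- Exempt SAEs and deaths from the 3-day exclusion, so that every treatment-emergent SAE and death collected after the first dose is counted by arm, under one rule, in both the SAE display and the SAE-proportion summary.
- State that the proportion summary covers all SAEs, and show SAEs and adverse events leading to discontinuation separately.
- Keep the 3-day window for the routine treatment-emergent adverse event tables.

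This needs no new data collection and no new type of table. SAP 1.2 allows changes to statistical methods before database lock to be documented in the SAP without a protocol amendment. The downside is that a few off-drug background events will be counted as SAEs, under the same rule in both arms.

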1.4.2. Laboratory Data

Clinical Laboratory Data

The summary statistics of raw data (hematology and chemistry) and change from baseline values will be presented, as well as shift tables from baseline to post-baseline values using normal ranges. For urinalysis parameters, the number and percentage of patients falling under each category of the test will be presented.

Clinical laboratory data will be summarized for each treatment group by presenting the proportions of patients with clinically notable abnormalities ([Appendix 24.1](#)).

Clinically notable values will be identified according to the criteria identified in the FDA's "Supplementary Suggestions for Preparing an Integrated Summary of Safety Information in an Original NDA Submission and for Organizing Information in Periodic Safety Updates" (Revised 2-APR-87) provided by the FDA Division of Neuropharmacological Drug Products (DNDP). Differences in incidence rates between the treatment groups will be tested as described in the SAP.

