 - a. An investigational drug, including placebo, within 8 weeks or within 5 half-lives (if-known), whichever is longer, prior to the baseline visit or
 - b. An AD or immune-related biologic for less than 5 half-lives (if known) or 16 weeks prior to the baseline visit.

- c. Note: For clarity, an example of such biologics would be drugs such as dupilumab (approved by the FDA for treatment of AD) and fezakinumab (a biologic being investigated in AD).
- 6. Recent history (within six months of screening) of drug or alcohol abuse as defined in DSM-5 Diagnostic Criteria for Drug and Alcohol Abuse and/or a positive drug or alcohol screen at the Screening visit;
- 7. Patient has made a suicide attempt and/or had suicidal ideation of type 4 or 5 on the Columbia-Suicide Severity Rating Scale (C-SSRS) in the past 2 years, or patient is at risk of suicide at Screening or Baseline, in the opinion of the Investigator;
- 8. Any medical procedure requiring general anesthetic within three months of the Baseline Visit or any procedure requiring sedation within one month of the baseline visit;
- 9. Current clinically significant cardiovascular, respiratory, neurologic, hepatic, hematopoietic, renal, gastrointestinal, or metabolic dysfunction unless currently controlled and stable, including (but not limited to) the following:
 - a. Uncontrolled diabetes mellitus defined as HbA1c > 7%;
 - b. Positive hepatitis C antibody test (anti-HCF);
 - c. Positive hepatitis B surface antigen (HBsAg).
- 10. History (including family history) or current evidence of congenital long QT syndrome or known acquired QT interval prolongation;
- 11. History of intolerance and/or hypersensitivity to medications similar to tradipitant and its accompanying excipients;
- 12. Indication of impaired liver function (values for AST, ALT, or bilirubin > 2 times the Upper Limit of Normal (ULN));
- 13. Has a creatinine level > 1.25x ULN;
- 14. Randomization in a previous tradipitant clinical trial;
- 15. Anyone affiliated with the site or sponsor and/or anyone who may consent under duress;
- 16. Any other sound medical reason as determined by the Investigator including any condition which may lead to an unfavorable risk-benefit of study participation, may interfere with study compliance or may confound study results.

Investigational Product, Dosage, and Mode of Administration:

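### The normal-range shift table for liver tests cannot show worsening in patients who enter between 1x and 2x ULN and does not grade rises in the others; add ULN-multiple and joint enzyme-bilirubin displays.

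*SAP*

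**What the plan says.** **Entry.** Protocol Synopsis, exclusion criterion 12, sets the liver limit at "values for AST, ALT, or bilirubin > 2 times the Upper Limit of Normal (ULN"). Values above 1x and up to 2x ULN are therefore admissible.

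**Follow-up.** Under Protocol Table 1, footnote 4, raised liver enzymes at any visit lead to "an unscheduled visit to redraw chemistry and coagulation samples will be completed prior to the next scheduled visit". Table 1 schedules post-baseline chemistry at V3, V4 and V6 (Days 14, 28 and 56).

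**Displays.** SAP 1.4.2 plans three for chemistry:
- Summary statistics: "The summary statistics of raw data (hematology and chemistry) and change from baseline values will be presented".
- A shift display: "shift tables from baseline to post-baseline values using normal ranges".
- A threshold display by arm, "presenting the proportions of patients with clinically notable abnormalities". Its limits come from Appendix 24.1 and a named FDA document, neither of which is in the supplied text. Between-arm testing is planned but deferred: "Differences in incidence rates between the treatment groups will be tested as described in the SAP".

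SAP 1.4 places the frequency of clinically notable laboratory values in the primary safety assessment and lists changes in laboratory values among the other evaluations.

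**The concern.** A shift table is meant to show who got worse relative to where they started. With normal-range categories, a patient who enters above ULN is already in the top category and cannot move up, whatever happens on drug. A patient who enters normal can move up, but a marginal crossing of ULN and a large rise fall in the same cell.

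The protocol gives liver tests particular attention, with an entry limit in multiples of ULN and a compulsory redraw, yet the laboratory section does not carry that scale into the tables. Elsewhere the plan looks for worsening as well as new onset: SAP 1.4.1 does so for adverse events and SAP 1.4.4 for ECG abnormalities. At stake is how readily a small liver signal can be seen with 100 patients per arm.

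**Working it through.** The plan states no figure on this point, so there is none to reproduce. The check is one of classification, followed by assumed examples to show scale.

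**1. How individual patients are classified.** Inputs: the 2x ULN entry limit (exclusion 12) and the normal-range rule (SAP 1.4.2), taking high as above 1x ULN. The patient values are illustrative.

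| Baseline to post-baseline (x ULN) | Normal-range shift | Bands ≤1, >1-2, >2-3, >3-5, >5 |
|---|---|---|
| 0.9 to 1.1 | Normal to High | ≤1 to >1-2 |
| 0.9 to 8 | Normal to High | ≤1 to >5 |
| 1.5 to 1.6 | High to High | no change |
| 1.9 to 6 | High to High | >1-2 to >5 |
| 2.0 to 10 | High to High | >1-2 to >5 |

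The normal-range table merges rows 1 and 2, and merges rows 3 to 5. The banded table separates the trivial from the marked rises in both groups.

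**2. How many patients could be affected.** The documents do not say. If 5% to 15% entered between 1x and 2x ULN (an assumption), that would be 0.05 × 200 = 10 to 0.15 × 200 = 30 patients.

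**3. What a reader would see by arm.** Assume 100 per arm (SAP 1.1), 10 trivial normal-to-high shifts in each arm, and 4 marked rises on drug only. P-values are two-sided Fisher exact.

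| Of the 4, entered high | Shift table, drug v placebo | p | Count of marked rises | p |
|---|---|---|---|---|
| 0 | 14 v 10 | 0.51 | 4 v 0 | 0.12 |
| 2 | 12 v 10 | 0.82 | 4 v 0 | 0.12 |
| 4 | 10 v 10 | 1.00 | 4 v 0 | 0.12 |

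A smaller case gives the same picture. If ULN is the 97.5th percentile and the three scheduled draws are independent, 1 - 0.975³ = 0.073 of patients normal at entry would cross by chance, about 7 per 100 and fewer if draws are correlated. Three marked rises on drug, all entering normal, then read 10 v 7 (p = 0.61) in the shift table and 3 v 0 (p = 0.25) as a count.

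**4. Whether the summary statistics compensate.** Two rises of 4x ULN among 100 patients move the mean change by 2 × 4 / 100 = 0.08x ULN. The maximum, which SAP 1.2.1 requires, would show one extreme value but not how many patients had one.

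**5. Which post-baseline value is used.** SAP 1.4.2 does not say whether the shift uses each visit, the last value or the highest, nor whether unscheduled redraws count. SAP 1.2.1 defines endpoint as the last non-missing observation. If that rule governed the shift, a transient peak would not appear in it.

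**The case against.** The strongest reply is that the shift table does not stand alone. The clinically notable proportion is a threshold count by arm, belongs to the primary safety assessment, and does not depend on the shift category. A patient going from 1.9x to 8x ULN is counted there whenever the cut-off lies between those values, and in the example above that table could itself show 4 v 0. This stands. A reader might infer that marked elevations are lost from the analysis altogether; the documents do not support that. What remains open is how a patient already abnormal at baseline is counted, since SAP 1.4.2 does not describe the proportion as relative to baseline. The limits themselves cannot be judged, and their absence from the supplied text is not an error.

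Three further replies have force:
- SAP 1.2 describes itself as general and leaves full methodology to a later plan, so silence on ULN bands does not prove that none will be produced. The normal-range rule is nonetheless stated.
- A liver rise reported as an adverse event would be summarized under SAP 1.4.1, which includes worsening from baseline. That route depends on the rise being reported as an event.
- The examples rest on invented counts, and the preferred count is not significant either.

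Two other inferences should not be drawn. One is that coagulation redraws enter no summary: the first paragraph of SAP 1.4.2 names only hematology, chemistry and urinalysis, but its clinically notable sentence covers clinical laboratory data generally. The other is that patients entering above ULN are the ones most likely to worsen; nothing in the documents says so.

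**Conclusion.** The point holds for the shift table and is minor. Given exclusion 12 and the normal-range rule, that table cannot show worsening in anyone entering above 1x ULN, and it does not grade rises in anyone else. This follows from the text and needs no assumption. No display described in SAP 1.4.2 shows raised enzymes and raised bilirubin in the same patient.

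The practical size is unknown. It depends on the share entering above ULN and on the unseen clinically notable limits. The 5% to 15% range and the counts of marked and trivial rises are assumptions for illustration. The benefit of a better display is that a difference such as 4 v 0 can be seen, not that it would reach significance. The issue concerns reporting only and affects neither the primary endpoint nor data collection.

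**What to change.** Keep the normal-range shift table for all analytes. For AST, ALT and bilirubin, add to SAP 1.4.2:

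1. A by-arm shift from baseline to the highest on-treatment value, including unscheduled redraws, in multiples of ULN (for example ≤1, >1-2, >2-3, >3-5, >5).
2. A by-arm display of each patient's peak ALT/AST against peak bilirubin, both in multiples of ULN. The two peaks should not have to come from the same draw: scheduled chemistry is 14 to 28 days apart after baseline, so an enzyme peak and a later bilirubin rise could fall on different draws.

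Also state in one sentence how the clinically notable proportion counts a patient who is already abnormal at baseline.

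The cost is SAP wording and two more tables, with no new visits, samples or patients. The downside is small cell counts, which should be labelled descriptive because they will rarely reach significance.
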